## 10. SAFETY

The Sponsor's SOPs provide further detail on safety reporting.

### 10.1 Medical Device Category A studies

Device deficiencies and all **adverse events (AE)** including all **serious adverse events (SAE)** are collected, fully investigated and documented in the source document and appropriate case report form (CRF) during the entire study period, i.e. from patient's informed consent until the last protocol-specific procedure, including a safety follow-up period. Documentation includes dates of event, treatment, resolution, assessment of seriousness and causal relationship to device and/or study procedure [ISO 14155, 6.4.1].

The information on AEs is systematically collected by the PI at each study visit. They will follow the procedures outlined in SOP ID106\_AE Reporting. The subjects are asked at each appointment if they have experienced any events since the last appointment. During the appointments the subjects are then asked questions about the event to gather details and to determine the severity of the event. If a subject reports pain that results in the inability to use the device, he will be withdrawn from the study in order to avoid any pain from using the device and to remove partial data from the study. For reports of pain caused by insertion or the dome itself, the problem can be addressed in the clinic. For example, a different style or size of dome can be placed on the hearing aid, and re-training of insertion can be performed with the subject to avoid wrong or forceful insertion of the device. For reported pain they will be advised to not wear the device for 24 hours before resuming use.

Foreseeable adverse events outlined in the risk management file include discomfort caused by the domes, domes or filters falling off in the ear, no amplification coming from the device causing alarms or traffic to not be heard by the subject, skin reaction if chemical profile of device is changed, maximum output of the device exceeding 132 dB SPL, battery exploding or catching fire, swallowing of a lithium battery, and the device affecting other medical devices worn by the subject. The incidence of all of these risks or adverse events is improbable. To mitigate the risk, the IFU describes how to insert the device, how to change the domes, and how to change a battery in case of no amplification. The IFU describes how to clean the device, domes, and filters in order to not introduce cleaning agents that might change the chemical profile of the hardware of the device. The labelling warns of the potential maximum output of the device. The IFU instructs the user to keep the device away from explosive environments, and to keep them away from children or pets that might swallow the batteries. The IFU warns of interference with implantable devices.

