### **7.4 Criteria for withdrawal / discontinuation of participants**

Participants are allowed to withdraw from the study at any time and for any reason. They do not have to share the reasons with the investigator. They will be asked to return the IMD. If the decision to withdraw is made by the investigator, the PI will inform the subject in person that they are no longer needed for the study. Reasons for withdrawing a participant from the study could be for non-compliance during testing, unreliable responses, medical reasons such as an ear infection, or the study may need to be stopped or postponed. Any data gathered from these subjects will be used for the current study. All data will remain encoded because results are only recorded using the identification code of the subject. There are normally at least five “back-up” test participants on the list to replace those that withdraw or are withdrawn. The “back-up” participants will have already been screened and deemed to be appropriate for the study.

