## 8.3 Dose / Device modifications

The IMD will provide the amplification prescribed by the fitting rationale and will be measured with Real Ear Measures (REM). The SP and the IP will be programmed with the P1 gain as a reference with fine-tuning performed on the IP. Because the gain will be verified objectively and fine-tuned based on the patient's comments, it is not expected that any negative effects should be experienced that would make them want to discontinue use of the device. However, if a subject does report such differences, it will be possible to improve the programming with fine tuning. Fine tuning can improve the situation by making slight changes to the gain (higher or softer) enough for the subject to continue with the study. If the subject requests to discontinue they can immediately remove the IMD from their ear(s) and do not need to wait until their next appointment in order to do so. They will be asked to return the IMD to Bernafon AG, but their data will still be included in the results for the current study. All data will remain encoded because the results are only recorded using the identification code of the subject.

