## 8.5 Data Collection and Follow-up for withdrawn participants

Any data that is collected will be kept in the Smart Trial data management database. The data will remain encoded because results are only recorded using the identification code of the subject. The analysis and report will include a summarized section based on the data available from all recruited subjects and another section based on the data from the subjects that complete the entire protocol. Withdrawn subjects will have the same follow-up as those subjects that complete the trial. Those subjects that are taken from the Bernafon directory, including those that withdraw, are welcome to return to the clinic for fine-tuning and maintenance as needed.

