### **11.4 Planned Analyses**

#### **11.4.1 Datasets to be analysed, analysis populations**

Primary analysis of the primary outcome will be based on the intention-to-treat (ITT). The ITT population will include all participants with associated primary outcome data, excluding only subjects who were deemed ineligible following the screening visit, those who withdrew from the trial and were unwilling for their previously collected data to be utilised or those who failed to provide baseline.

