4.2 Analysis populations

The analysis of the primary outcome will be based on the intention-to-treat (ITT). The ITT population will include all participants with associated primary outcome data, excluding only subjects who were deemed ineligible following screening visit, those who withdrew from the trial, were unwilling for their previously collected data to be utilised or those who failed to provide baseline.

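### Protocol 10.1 makes removal of partial data a purpose of withdrawing participants for device pain, which contradicts the keep-the-data rule in 7.4 and could selectively thin the questionnaire-based safety and acceptance results

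*Protocol*

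**What the plan says.** Protocol 10.1 covers a participant who reports pain that makes the device unusable. That participant is withdrawn "to avoid any pain from using the device and to remove partial data from the study". No passage limits the removal to particular variables or exempts adverse event or questionnaire data.

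Other sections keep the data of withdrawn participants:

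- **Protocol 7.4.** The investigator's reasons for withdrawing someone include "non-compliance during testing, unreliable responses, medical reasons such as an ear infection". The rule for their data is "Any data gathered from these subjects will be used for the current study". The same section normally provides at least five back-up participants as replacements.
- **Protocol 8.3.** A participant who asks to stop returns the device, "but their data will still be included in the results for the current study".
- **Protocol 8.5.** Collected data stay in the database. "The analysis and report will include a summarized section based on the data available from all recruited subjects", with a second section for those who complete the protocol.
- **Protocol 11.4.1.** Among the exclusions from the primary analysis population are "those who withdrew from the trial and were unwilling for their previously collected data to be utilised". Withdrawal alone does not exclude.
- **SAP 4.2.** The matching phrase reads "those who withdrew from the trial, were unwilling for their previously collected data to be utilised", with a comma where the protocol has a conjunction.

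**The concern.** Participants who cannot wear the device because of pain have, by definition, had a poor device experience. Removing their data for that reason makes exclusion depend on an outcome, in a study whose objectives include device safety (protocol 4.4) and general acceptance of the hearing aids (protocol 4.3).

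Much of the safety and acceptance information comes from questionnaires. Protocol 5.3 and 9.2.3 place the questions on unexpected device behaviour there. SAP 6.1.4 adds physical comfort, feedback and sound quality, and SAP 6.2.4 uses the general questionnaire to evaluate safety. Protocol 6.1.3 uses P1 to tell dislike of the music programs from failure to accept the device at all, and that check weakens if those who could not wear the device are taken out. Replacement from the back-up list could bring the count back to the planned number and make the loss hard to see.

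**Working it through.** **1. Plan's own figure.** There is none to reproduce. The size of 18-20 was set from related studies and recruitment potential (protocol 11.2, SAP 3.3), and no rate of withdrawal for pain is given.

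**2. The rules side by side**

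| Section | Who is covered | Data | Against 10.1 |
|---|---|---|---|
| 10.1 | Pain prevents device use | Removal is a stated purpose | n/a |
| 7.4 | All withdrawals, including by the investigator for medical reasons | Used | Direct conflict |
| 8.5 | All recruited | Kept and summarised | Conflict with the all-recruited section; none with the completer section |
| 11.4.1 | Primary analysis population | Withdrawn are excluded only if they refuse use | Inconsistent |
| 8.3 | Those who ask to stop | Included | Same principle, different participants |

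**3. What a participant withdrawn for pain would have contributed** (protocol 7.3 and 9.3)

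- After visit 1: adaptive music perception (AMP) results, unaided and with P1.
- By visit 2: the P1 product and music questionnaires, filled in at home the day before. Someone who stops early in the first field period may have none.
- At visit 2: AMP with whichever music program is in position P2.
- At visit 3 only: AMP with P3, and the preference questionnaire.

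Before visit 3 there is no preference value and no IP-SP pair on the AMP. Those comparisons lose nothing further through removal, because a participant with missing data already drops out of that part of the analysis (protocol 11.5). What can be lost is the P1 questionnaires and the baseline and P1 AMP results.

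**4. Weight of one participant.** 1/20 = 5.0%; 1/18 = 5.6%.

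**5. Direction, on assumed inputs.** Let k = 1, 2 or 3 participants be withdrawn for pain out of N.

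*Questionnaire item*, 5 points with 1 best (protocol 9.2.2). Assume that those withdrawn returned the questionnaire and scored 5, and that the others average 2. Mean with data kept = (2(N - k) + 5k)/N = 2 + 3k/N.

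| N | k = 1 | k = 2 | k = 3 | Data removed |
|---|---|---|---|---|
| 20 | 2.15 | 2.30 | 2.45 | 2.00 |
| 18 | 2.17 | 2.33 | 2.50 | 2.00 |

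*Rate of pain that prevents use*, only if the adverse event records also left the tabulation. Kept: k/N. Removed: 0/(N - k). Intervals are exact 95%.

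| N = 20 | Kept | Removed |
|---|---|---|
| k = 1 | 5.0% (0.1-24.9) | 0/19, upper limit 17.6% |
| k = 2 | 10.0% (1.2-31.7) | 0/18, upper limit 18.5% |
| k = 3 | 15.0% (3.2-37.9) | 0/17, upper limit 19.5% |

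With replacement the removed column becomes 0/20, upper limit 16.8%. The observed rate is 0% whatever k is.

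**6. Chance that the rule is triggered at all.** P(at least one) = 1 - (1 - p)^N. For assumed true risks p of 2, 5, 10 and 15%, this is 33, 64, 88 and 96% at N = 20.

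**7. SAP 4.2 against protocol 11.4.1.** In the protocol, withdrawal and refusal must both apply before a participant is excluded. With the comma in the SAP they can be read as two separate grounds, so that every withdrawn participant is excluded. Both passages concern the primary outcome. Neither document defines a population for safety or acceptance.

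**The case against.** The strongest reply is that the clause in 10.1 is a purpose phrase in a safety narrative, not an analysis rule. The sections that govern data handling (7.4, 8.5, 11.4.1, 11.5) keep the data, and the SAP has no exclusion for pain. On that view this is a drafting slip. That may be so, and it means the bias is conditional. But nothing in the documents says which passage prevails, and 10.1 speaks of removal from the study, not from the completer summary. The completer section in 8.5 leaves these participants out already, so it does not explain the clause.

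Several stronger readings are tempting, and the documents do not support them:

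- *Adverse event counts will be lost.* Section 10.1 requires all adverse events to be documented throughout the study, 12.1.2 requires an eCRF for non-completers, and 11.4.5 and SAP 6.4 tabulate events without exclusions. Recording is protected. What remains open is that no passage says these records stay in the tabulation after a removal under 10.1.
- *Three sections contradict 10.1 equally.* Only 7.4 covers the case squarely. Section 8.3 concerns participants who ask to stop, and 8.5 conflicts only through its all-recruited summary.
- *Pain is rated likely in 10.1.1, so the effect will be large.* That rating covers any discomfort or pain, with remedies such as a change of dome. The trigger in 10.1 is narrower, and 10.1 itself calls its listed events, dome discomfort among them, improbable.
- *The comparison of IP with SP is biased.* Step 3 of the working shows that it is essentially untouched.

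**Conclusion.** The concern holds as a contradiction with a conditional consequence. Section 10.1 cannot be reconciled with 7.4 as written, and it is inconsistent with 8.5 and 11.4.1. If 10.1 is followed, and at least one participant is withdrawn for pain after contributing data, questionnaire-based safety and acceptance summaries would tend to favour the device, and the baseline and P1 AMP results would lose the same participants.

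The size cannot be fixed from the documents. Each participant carries 5-6% of the sample. The shifts in the working rest on assumed counts, scores and risks and show direction only. A reader might infer that the trial's safety results are biased; the documents support only that they could be, through the questionnaires. Confidence is high for the conflict of wording and lower for any effect on results.

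**What to change.** 1. In protocol 10.1, delete the closing clause on removing partial data.
2. State once, and refer to it from 7.4, 8.3 and 8.5, that adverse event, device-deficiency, questionnaire and AMP data collected up to withdrawal are kept and analysed unless the participant refuses use of their data.
3. Define the denominator for safety and acceptance summaries as all fitted participants, including those later replaced, and report withdrawals for pain separately from their replacements.
4. In SAP 4.2, restore the conjunction so that the exclusion matches protocol 11.4.1.

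The cost is one deleted clause, a sentence or two, and one word in the SAP. No extra visits, measurements or participants are needed. This concerns data handling only; the clinical rule for withdrawing a participant with pain is not commented on.

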#### 10.1.1 Foreseeable adverse events and anticipated adverse device effects

No serious adverse events are anticipated. The hearing aid was tested before release to market for safety and has been on the market with no reported problems for almost one year. The following is a list of common and expected adverse device effects.

Headache	Likely	No treatment, self-medication with analgesic, remove device for a period, reduce gain
Sounds are too loud	Likely	Reduce gain, remove device for a period
Tinnitus	Likely	Reduce gain, remove device for a period
Discomfort or pain from device in or around ear	Likely	Remove device and refrain from using for a period, change of dome, change of speaker length
Habituation to the hearing aids and a possible new hearing	Likely	Continued use of hearing aids after the trial is finished.

perception.		
-------------	--	--

### 10.1.2 Definition and Assessment of (Serious) Adverse Events and safety related events

#### Adverse Event (AE)

Any untoward medical occurrence, unintended disease or injury or any untoward clinical signs (including an abnormal laboratory finding) in participants, users or other persons whether or not related to the investigational medical device [ISO 14155: 3.2].

This includes events related to the investigational device or the comparator and to the procedures involved. For users or other persons this is restricted to events related to the investigational medical device.

#### Adverse Device Effect (ADE)

Adverse event related to the use of an investigational medical device [ISO 14155: 3.1].

This includes any adverse event resulting from insufficient or inadequate instructions for use, deployment, implantation, installation, operation, or any malfunction of the investigational medical device. This includes any event that is a result of a use error or intentional misuse.

Serious Adverse Event (SAE) [European regulation on medical devices 2017/745, art. 58].

Any adverse event that led to any of the following:

- (a) death,
- (b) serious deterioration in the health of the subject that resulted in any of the following:
  - (i) life-threatening illness or injury,
  - (ii) permanent impairment of a body structure or a body function,
  - (iii) hospitalisation or prolongation of patient hospitalisation,
  - (iv) medical or surgical intervention to prevent life-threatening illness or injury or permanent impairment to a body structure or a body function,
  - (v) chronic disease,
- (c) foetal distress, foetal death or a congenital physical or mental impairment or birth defect.

This includes device deficiencies that might have led to a serious adverse event if a) suitable action had not been taken or b) intervention had not been made or c) if circumstances had been less fortunate. These are submitted to the EC via BASEC within 7 days. A planned hospitalisation for pre-existing condition, or a procedure required by the protocol, without a serious deterioration in health, is not considered to be a serious adverse event.

#### Device deficiency

Inadequacy of a medical device related to its identity, quality, durability, reliability, safety or performance, such as malfunction, misuse or use error and inadequate labelling [ISO 14155: 3.15].

#### Health hazards that require measures

Findings in the trial that may affect the safety of study participants and, which require preventive or corrective measures intended to protect the health and safety of study participants SAE [ClinO Art. 37].

Causal Relationship of SAE [MEDDEV 2.7/3 revision 3, May 2015].

A causal relationship towards the medical device or study procedure should be rated as follows:

- **Not related:** The relationship to the device or procedures can be excluded.
- **Unlikely:** The relationship with the use of the device seems not relevant and/or the event can be reasonably explained by another cause, but additional information may be obtained.
- **Possible:** The relationship with the use of the investigational device is weak but cannot be ruled out completely. Alternative causes are also possible.
- **Probable:** The relationship with the use of the investigational device seems relevant and/or the event cannot be reasonably explained by another cause.

- **Causal relationship:** The serious event is associated with the investigational device or with procedures beyond reasonable doubt.

Device deficiencies that might have led to an SAE are always related to the medical device.

#### **10.1.3 Reporting of (Serious) Adverse Events and other safety related events**

Reporting to Sponsor-Investigator:

All SAEs, device deficiencies and health hazards that require measures are reported to the Sponsor-Investigator within 24 hours upon becoming aware of the event. Device deficiencies are assessed regarding their potential to lead to an SAE.

Pregnancies – No pregnant participants will be included in the study

Reporting to Authorities:

In Category A studies, the sponsor is subject to the notification requirements specified in Art. 15 of the MedDO of 17 October 2011 (SR 812.213).

It is the Investigator's responsibility to report to the Ethics Committee via BASEC **device deficiencies** that could have led to serious adverse events if suitable action had not been taken, intervention had not been made, or circumstances had been less fortunate within 7 days [ClinO Art. 42].

**Health hazards** that require measures are reported to the Ethics Committee via BASEC within 2 days [ClinO Art. 37].

Periodic safety reporting:

A yearly safety update-report is submitted by the Investigator to the Ethics Committee via BASEC.

A report is submitted to Swissmedic by the Sponsor-Investigator, as defined in Art. 15a, b of the MedDO of 17 October 2011 (SR 812.213).

## 11. STATISTICAL METHODS

### 11.1 Hypothesis

The assumption is that hearing aids that are optimized for hearing-impaired musicians should provide a better experience while playing an instrument with the following consequences: (a) improvement of the perception of music, (b) improvement of the ability to play, and (c) indirect improvement of the quality of life.

In summary, the primary reason for this study is to evaluate the new fitting protocol for musicians using hearing aids. The secondary reason is to evaluate the overall safety of the IMD by testing for unexpected behaviour from the IMD and by the collection of AEs to identify any new risk factors since their release to the market as a post-market quality control.

More specifically, the objective of the trial is to provide answers to following research questions:

- Does the fitting protocol optimized for hearing-impaired musician's individual needs make an audible difference compared to a standard fitting approach?
- Is the fitting protocol optimized for hearing-impaired musician's individual needs preferred over the standard fitting approach?
- Does the fitting protocol optimized for hearing-impaired musician's individual needs improve the perception of music compared to a standard fitting approach?

Null hypothesis: there is no audible difference or preference between the SP and the IP when the participants are playing or listening to music.

Alternative hypothesis: there is an audible difference or preference between the SP and the IP when the participants are playing or listening to music.

### 11.2 Determination of Sample Size

Vaisberg et al. (2018) is the only publication, to our knowledge, specifically focusing on hearing aids for hearing impaired musicians. They used a qualitative research methodology based on semi-structured interviews with 12 participants. Fullford et al. (2011) and Fullford & Ginsborg (2014) also used 12 participants for qualitative research studies about how hearing-impaired musicians experience sound and communicate while playing music. However, these publications are based on qualitative research methods which cannot be directly used for the sample size estimation.

Please refer to the Statistical Analysis Plan (SAP) for a complete list of articles used to determine the sample size. The SAP summarizes the sample sizes and population attributes from quantitative research tests in a lab, i.e. exclusion of online questionnaire-based research, with a topic related to the current study.

The sample size ranges between 9 and 21 participants when looking at studies including hearing aid users with a certain amount of musical training. This range can be used as a baseline for the sample size determination. However, there are some known limitations when using these references. Their study designs only include tests where the participants listen to predefined music samples and not when they are playing their own musical instruments. The definition of the sample size for this exploratory trial should take the population homogeneity and the recruitment potential into account.

On one hand, arguments for a sample size closer to the lower boundary might be justified by a relative homogeneous population reflecting a strong external validity potential because:

- The hearing loss is within the fitting ranges of the IMD, i.e. exclusion of participants with a too mild or profound hearing loss degree,
- The musical experience and practice are set as inclusion criteria, i.e. participants are regularly playing an instrument in different groups or ensembles,
- The recruitment process is restrictive. The target population must fulfil the inclusion /

exclusion criteria and be ready to bring their own instrument for the IP fitting. These criteria will eliminate potential participants with cognitive, social, or physical difficulties.

On the other hand, there are some unknown parameters that have also to be considered for the sample size determination:

- The effect of the instrument, i.e. the sound generation principle greatly varies between a string, a woodwind and a brass instrument. This might affect the perception of sound and interact with the range of the instrument, the hearing loss degree and type,
- The effect of amplification through hearing aids when musicians are playing. All the above-mentioned tests are based on passive listening experience. There are no publications, to the best of our knowledge, about the use of auditory feedback to control the production of music. We can assume that adaptation of their own voice production to the environment (Lombard effect) and perception of sound might show similarities when playing music,
- The effect of the IP which follows guidelines for hearing aids fitted to musicians. The guidelines are based on a project (Greasley et al., 2019) but no results based on quantitative research were published. It is therefore not possible to estimate an effect size when a personalized protocol like the IP is used with musicians.

The uncertainty from the test design and the unknown effect size from the IP motivates the choice for a larger sample size. Regarding recruitment possibilities, based on the principal investigator's input, the sample size was set to 18-20 participants for the current study.

